**Table 7: Proposed Modified International Working Group Response Criteria for Acute Myeloid Leukemia**

Category	Definition
Complete remission (CR)*	Bone marrow blasts <5 percent; absence of blasts with Auer rods; absence of extramedullary disease; absolute neutrophil count >1.0 x 10  /L (1000/μL); platelet count >100 x 10  /L (100,000/μL); independence of red cell transfusions
CR with incomplete platelet recovery (CRp)	All CR criteria except for residual thrombocytopenia (platelet counts <100 x 10  /L [100,000/μL])
CR with incomplete recovery (CRi)•	All CR criteria except for residual neutropenia (absolute neutrophil count <1.0 x 10  /L [1000/μL])
Cytogenetic CR (CRc)◇	Reversion to a normal karyotype at the time of morphologic CR (or CRi) in cases with an abnormal karyotype at the time of diagnosis; based on the evaluation of 20 metaphase cells from bone marrow
Molecular CR (CRm)§	No standard definition; depends on molecular target
Morphologic leukemia-free stateΔ	Bone marrow blasts <5 percent; absence of blasts with Auer rods; absence of extramedullary disease; no hematologic recovery required
Partial remission (PR)	Relevant in the setting of phase I and II clinical trials only; all hematologic criteria of CR; decrease of bone marrow blast percentage to 5 to 25 percent; and decrease of pretreatment bone marrow blast percentage by at least 50 percent
Treatment failure	
Resistant disease (RD)	Failure to achieve CR or CRi (general practice; Phase 2/3 trials), or failure to achieve CR, CRi or PR (Phase 1 trials); only includes patients surviving ≥7 days following completion of initial treatment, with evidence of persistent leukemia by blood and/or bone marrow examination
Death in aplasia	Deaths occurring ≥7 days following completion of initial treatment while cytopenic; with an aplastic or hypoplastic bone marrow obtained within 7 days of death, without evidence of persistent leukemia
Death from indeterminate cause	Deaths occurring before completion of therapy, or <7 days following its completion; or deaths occurring ≥7 days following completion of initial therapy with no blasts in the blood, but no bone marrow examination available
Relapse (defined only for subjects who have previously attained CR, CRi, CRp or MLFS)‡	Bone marrow blasts ≥5 percent; or reappearance of blasts in the blood; or development of extramedullary disease

Source: (Cheson, et al. 2003)

Footnotes on next page

\* All criteria need to be fulfilled; marrow evaluation should be based on a count of 200 nucleated cells in an aspirate with spicules; if ambiguous, consider repeat exam after 5 to 7 days; flow cytometric evaluation may help to distinguish between persistent leukemia and regenerating normal marrow; a marrow biopsy should be performed in cases of dry tap, or if no spicules are obtained; no minimum duration of response required.

• The criterion of CRi is of value in protocols using intensified induction or double induction strategies, in which hematologic recovery is not awaited, but intensive therapy will be continued. In such protocols, CR may even not be achieved in the course of the entire treatment plan. In these instances, the overall remission rate should include CR and CRi patients. Some patients may not achieve complete hematologic recovery upon longer observation times.

Δ This category may be useful in the clinical development of novel agents within phase I clinical trials, in which a transient morphologic leukemia-free state may be achieved at the time of early response assessment.

(Footnotes continued on next page)

◇ Four studies showed that failure to convert to a normal karyotype at the time of CR predicts inferior outcome.

§ As an example, in core-binding factor AML low-level polymerase chain reaction-positivity can be detected in patients even in long-term remission. Normalizing to 104 copies of ABL1 in accordance with standardized criteria, transcript levels below 10 to 12 copies appear to be predictive for long-term remission.

¥ -. A repeat marrow should be performed to confirm relapse with 2 consecutive assessments separated by at least 1 month. Appearance of new dysplastic changes should be closely monitored for emerging relapse. In a patient who has been recently treated, dysplasia or a transient increase in blasts may reflect a chemotherapy effect and recovery of hematopoiesis. Cytogenetics should be tested to distinguish true relapse from therapy-related MDS/AML.

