**Figure 7: Dose Escalation Scheme**

\*If only 3 subjects were enrolled at the MTD level, an additional 3 subjects will be enrolled to confirm that <2 of 6 subjects experiences a DLT at this dose.

Note: CST = Clinical Study Team; DLT = dose-limiting toxicity; MTD = maximum tolerated dose.

Candidates for the dose-escalation phase of the study are adult subjects, 18 years of age or older, with:

- Diagnosis of AML according to WHO criteria ([Appendix 15.1](#));
  - o Disease refractory or relapsed (defined as the reappearance of > 5% blasts in the bone marrow, see [Table 7](#) and [Table 8](#)) or
  - o Untreated AML, ≥60 years of age and not candidates for standard therapy due to age, performance status, and/or adverse risk factors, according to the treating physician and with approval of the Medical Monitor;
- Diagnosis of Myelodysplastic syndrome with refractory anemia with excess blasts (subtype RAEB-1 or RAEB-2), or considered high-risk by the Revised International

Prognostic Scoring System (IPSS-R) ([Appendix 15.3](#)) ([Greenberg, et al. 2012](#)), that is recurrent or refractory, or the subject is intolerant to established therapy known to provide clinical benefit for their condition (i.e., subjects must not be candidates for regimens known to provide clinical benefit), according to the treating physician and with approval of the Medical Monitor. Subjects with other relapsed and/or primary refractory hematologic cancers, for example chronic myelomonocytic leukemia (CMML), who fulfill the inclusion/exclusion criteria may be considered on a case-by-case basis, with approval of the Medical Monitor.

Confirmation of the primary malignancy is required. Subjects in the dose escalation phase are required to have IDH2 gene-mutated disease, documented by local site testing. Retrospective gene mutation analysis will be conducted at a central laboratory to support contemporaneous companion diagnostic development.

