### 7.1.2. Overview of the Phase 1/Part 1 Expansion

A dose of 100 mg QD has been selected for initial evaluation in Part 1 Expansion (see [Section 7.3.2.](#)). Different dosing regimens may be explored within the expansion phase of the study if warranted based on the emerging clinical safety, PK, PD and clinical activity data. During the expansion phase, safety, PK/PD, and preliminary clinical activity data will be reviewed by the Clinical Study Team every 8 weeks.

Part 1 Expansion phase will enroll approximately a minimum of 100 subjects divided into 4 non-randomized arms of approximately a minimum of 25 subjects per arm with IDH2-mutated hematologic malignancies as follows:

- Arm 1: Relapsed or refractory AML (Table 7 and Table 8) and age  $\geq 60$  years, or any subject with AML regardless of age who has relapsed following a BMT.
- Arm 2: Relapsed or refractory AML (Table 7 and Table 8) and age  $< 60$  years, excluding subjects with AML who have relapsed following a BMT.
- Arm 3: Untreated AML and age  $\geq 60$  years that decline standard of care chemotherapy.
- Arm 4: IDH2-mutated advanced hematologic malignancies not eligible for Arms 1 to 3.

As in the dose escalation phase, subjects in Part 1 Expansion are required to have IDH2 gene-mutated disease documented by local site testing with retrospective gene mutation analysis conducted at the central laboratory.

### 7.1.3. Overview of Phase 2

Based on continued ongoing demonstration of safety and clinical activity in the dose escalation portion of the study, the Phase 2 portion of the trial will further establish the clinical activity and safety profile of AG-221 in subjects with relapsed or refractory AML that harbor an IDH2 mutation .

The Phase 2 portion of the trial will enroll approximately 125 subjects with IDH2-mutated relapsed or refractory AML defined as follows (Table 7 and Table 8):

- Subjects who relapse after allogeneic transplantation
- Subjects in second or later relapse
- Subjects who are refractory to initial induction or re-induction treatment

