### **Phase 2:**

- Diagnosis of AML according to World Health Organization (WHO) criteria ([Appendix 15.1](#)) and disease relapsed or refractory as defined by ([Table 7](#) and [Table 8](#)):
    - Subjects who relapse after allogeneic transplantation;
    - Subjects in second or later relapse;
    - Subjects who are refractory to initial induction or re-induction treatment;
3. Subjects who relapse within 1 year of initial treatment, excluding patients with favorable-risk status according to NCCN Guidelines ([NCCN 2015](#)). Favorable-risk cytogenetics: inv(16), +(16;16), t(8;21), t(15;17). Subjects must have documented IDH2 gene-mutated disease:
- For subjects in the dose escalation phase and Part 1 Expansion, IDH2 mutation may be based on local evaluation. (Centralized testing will be performed retrospectively.)
  - For subjects in the Phase 2 portion of the trial, central testing of IDH2 mutation of bone marrow aspirate **and/or** peripheral blood, is required during screening to confirm eligibility.

4. Subjects must be amenable to serial bone marrow sampling, peripheral blood sampling, and urine sampling during the study.
  - The diagnosis and evaluation of AML or MDS will be made by bone marrow aspiration and/or biopsy. If an aspirate is unobtainable (i.e., a “dry tap”), the diagnosis may be made from the core biopsy.
  - Screening bone marrow aspirate **and** peripheral blood samples are required all subjects. A bone marrow biopsy must be collected if adequate aspirate is not attainable unless:
    - A bone marrow aspirate and biopsy was performed as part of the standard of care within 28 days prior to the start of the study treatment; and
    - Slides of bone marrow aspirate, biopsy and stained peripheral blood smear are available for both local and central pathology reviewers; and
    - A bone marrow aspirate sample acquired within 28 days prior to the start of study treatment has been sent for cytogenetic analysis.
5. Subjects must be able to understand and willing to sign an informed consent. A legally authorized representative may consent on behalf of a subject who is otherwise unable to provide informed consent, if acceptable to and approved by the site and/or site’s Institutional Review Board (IRB)/Independent Ethics Committee (IEC).
6. Subjects must have ECOG PS of 0 to 2 ([Appendix 15.5](#)).

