8.2.1. Baseline Disease Characteristics

1. ECOG PS at baseline (Grade 0, 1, 2, 3, or 4).
2. Gene mutation (IDH2) analysis at baseline (R140Q or R172K, or Unknown) (Local and Central).
3. UGT1A1 mutation status (heterozygous, homozygous, wild type, and NA).
4. R/R AML subtype (subjects who relapse after allogeneic transplantation; subjects in second or later relapse; subjects who are refractory to initial induction or re-induction treatment; subjects who relapse within 1 year of initial treatment, excluding subjects with favorable-risk status according to [National Comprehensive Cancer Network \[NCCN\] Guidelines \[NCCN v1.2015\]](#). Favorable-risk cytogenetics: inv(16), +(16;16),

t(8;21), t(15;17); subjects who have failed 2 or more cycles of first line therapy [consisting of an intermediate intensity chemotherapy, hypomethylating agent, or low dose cytarabine]).

5. Refractory/relapse status (primary refractory and relapse)
6. Prior systemic anti-cancer therapies for disease under investigation. (yes vs no).
7. Number of prior anti-cancer regimens (1, 2, 3, 4, and ≥ 5).
8. Prior stem cell transplants for AML (yes vs no); transplant type if yes (autologous, allogenic, other).
9. Cytogenetic risk status (favorable-risk, intermediate-risk, poor-risk, or failure).
10. Time (month) from last prior HSCT, calculated from starting date of prior HSCT to the first dose of AG-221.
11. Bone marrow blasts (%) and category (<20%; 20% to <30%; 30% to <50%; $\geq 50\%$) from the screening bone marrow aspirate/biopsy sample. Bone marrow aspirate will be used as the primary source. If no aspirate assessment is available, biopsy assessment will be used as default.
12. Peripheral blood blast (%).
13. Baseline values of the following lab parameters: Hemoglobin (<80 g/L, ≥ 80 g/L), platelet count (< $50 \times 10^9/L$, $\geq 50 \times 10^9/L$), absolute neutrophil count (ANC) (< $0.5 \times 10^9/L$, 0.5 to < $1 \times 10^9/L$, $\geq 1.0 \times 10^9/L$), white blood cells (WBC) (< $15 \times 10^9/L$, 15 to < $30 \times 10^9/L$, $\geq 30 \times 10^9/L$), creatinine clearance (<45 mL/min, 45 to <60 mL/min, ≥ 60 mL/min). These lab parameters will be summarized using descriptive statistics (number of subjects, mean, SD, median, minimum, and maximum) as well.

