Death from indeterminate cause	Deaths occurring before completion of therapy, or < 7 days following its completion; or deaths occurring ≥ 7 days following completion of initial therapy with no blasts in the blood, but no bone marrow examination available
Relapse (defined only for subjects who have previously attained CR, CRi, CRp or MLFS)	Bone marrow blasts ≥ 5 percent; or reappearance of blasts in the blood; or development of extramedullary disease

Source: ([Cheson, et al. 2003](#))

Footnotes on next page

- * All criteria need to be fulfilled; marrow evaluation should be based on a count of 200 nucleated cells in an aspirate with spicules; if ambiguous, consider repeat exam after 5 to 7 days; flow cytometric evaluation may help to distinguish between persistent leukemia and regenerating normal marrow; a marrow biopsy should be performed in cases of dry tap, or if no spicules are obtained; no minimum duration of response required.
- The criterion of CRi is of value in protocols using intensified induction or double induction strategies, in which hematologic recovery is not awaited, but intensive therapy will be continued. In such protocols, CR may even not be achieved in the course of the entire treatment plan. In these instances, the overall response rate should include CR and CRi patients. Some patients may not achieve complete hematologic recovery upon longer observation times.
- Δ This category may be useful in the clinical development of novel agents within Phase I clinical trials, in which a transient morphologic leukemia-free state may be achieved at the time of early response assessment.
- ◇ Four studies showed that failure to convert to a normal karyotype at the time of CR predicts inferior outcome.
- § As an example, in core-binding factor AML low-level polymerase chain reaction-positivity can be detected in patients even in long-term response. Normalizing to 104 copies of ABL1 in accordance with standardized criteria, transcript levels below 10 to 12 copies appear to be predictive for long-term response.

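### A Phase 2 subject with blood blasts but marrow blasts below 5% could already meet MLFS at entry and count in the primary ORR with unchanged disease

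*Protocol*

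**What the plan says.** **Entry.** Protocol Section 7.1.3 plans "approximately 125 subjects with IDH2-mutated relapsed or refractory AML defined as follows (Table 7 and Table 8"), and the Phase 2 part of Section 8.2 likewise requires "disease relapsed or refractory as defined by" those tables. In Table 7, marrow blasts of 5% or more are one of three alternative ways to show relapse. The other two are "or reappearance of blasts in the blood; or development of extramedullary disease". SAP Table 6 (Section 15.3) repeats the row: "Bone marrow blasts ≥ 5 percent; or reappearance of blasts in the blood; or development of extramedullary disease". Resistant disease also needs no marrow finding; it is failure to respond "with evidence of persistent leukemia by blood and/or bone marrow examination". Only the dose-escalation criterion (Protocol Sections 7.1.1 and 8.2) adds a marrow threshold, with relapse "defined as the reappearance of > 5% blasts in the bone marrow". A footnote to Table 7 says a repeat marrow should confirm relapse, but gives no blast percentage.

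**Response.** MLFS is "Bone marrow blasts <5 percent; absence of blasts with Auer rods; absence of extramedullary disease; no hematologic recovery required". CR has the same marrow, Auer-rod and extramedullary items, and adds neutrophil, platelet and red cell transfusion conditions. CRp and CRi each relax one count. None of the four mentions circulating blasts or a change from baseline.

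**Use.** Protocol Section 12.5.7 and SAP Section 10.2 count MLFS in the primary ORR. Phase 2 is judged by whether the exact 95% lower bound exceeds 25%. SAP Section 8.2.1 item 11 tabulates "Bone marrow blasts (%) and category (<20%; 20% to <30"% and upward, so its lowest class does not separate subjects below 5%.

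**The concern.** A response rate should count disease that improved. The Phase 2 entry rule and the MLFS rule overlap. Someone who qualified on blasts in the blood, with marrow blasts below 5%, no Auer-rod blasts and no extramedullary disease, satisfies MLFS before the first dose. If nothing has changed at Cycle 2 Day 1, the written rule makes that subject a responder.

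Other definitions in the same protocol avoid this. PR and the MDS marrow CR need at least a 50% fall in marrow blasts, and MDS CR needs blood blasts of zero. The planned checks do not remove the problem either. The EAS exclusions (SAP Section 5.2.4) include no marrow-blast minimum, and the IRAC applies the same modified IWG criteria (SAP Section 15.3).

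At stake is the Phase 2 ORR and its 25% rule, which could be met partly by subjects whose disease did not move.

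**Working it through.** **Inputs.** N = 125, the success count of 42, the 25% reference rate and the stated interval come from Protocol Section 12.1. The exact two-sided 95% interval comes from SAP Section 10.2. The number k of subjects who meet MLFS at entry and are scored as responders is in neither document. Values of 1 to 5 are an assumption used to show the range.

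**Step 1: reproduce the plan's figure.** The Clopper-Pearson lower limit is the 0.025 quantile of Beta(x, n − x + 1), and the upper limit is the 0.975 quantile of Beta(x + 1, n − x). For x = 42 and n = 125 the rate is 42/125 = 33.6%, with limits 25.4% and 42.6%, as the protocol states. For x = 41 the lower limit is 24.7%, so 42 is the smallest passing count. The threshold itself is correct.

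**Step 2: a result at the threshold.** Start from 42/125. Keep the k subjects in the denominator but do not count them as responders.

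| k | Responders / N | Lower 95% limit | Above 25%? |
|---|---|---|---|
| 0 | 42/125 | 25.4% | yes |
| 1 | 41/125 | 24.7% | no |
| 2 | 40/125 | 23.9% | no |
| 3 | 39/125 | 23.2% | no |
| 5 | 37/125 | 21.8% | no |

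Dropping one such subject from both numerator and denominator gives 41/124, with a lower limit of 24.9%, which also fails. Each subject contributes 1/125 = 0.8 percentage points. A result with m responders to spare (42 + m) would need m + 1 such subjects to reverse it.

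**Step 3: chance of passing when the drug does no better than 25%.** Treat the k subjects as certain responders and let the other 125 − k respond independently at 25%. The chance of passing is P(X ≥ 42 − k), with X binomial(125 − k, 0.25).

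| k | Chance of reaching 42/125 |
|---|---|
| 0 | 1.9% |
| 1 | 2.7% |
| 2 | 3.7% |
| 3 | 5.0% |
| 5 | 8.7% |

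These are upper figures for each k. A real subject must also have an evaluable later marrow that is still below 5%, with no Auer-rod blasts and no extramedullary disease.

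**The case against.** The ordinary route into Phase 2 is marrow disease. Inclusion criterion 4 bases AML diagnosis and evaluation on marrow sampling, the relapse footnote asks for a repeat marrow, and the Medical Monitor confirms every subject's eligibility (Protocol Section 8.4). The dose-escalation text cites the same two tables while describing relapse as a marrow finding. This makes such entries less likely. It does not exclude them, because none of it sets a marrow percentage for Phase 2.

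The plan also gives some visibility. Best response is tabulated by category, the rates of CR, CR/CRh and CR/CRi/CRp leave MLFS out, and baseline marrow and blood blasts are listed by subject. A reader could find these subjects by hand. No planned analysis, however, tests the 25% rule without them.

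Three stronger readings are tempting, and the documents do not support them:

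- **That CR, CRi, CRp and MLFS all need nothing beyond marrow blasts below 5%.** All four also exclude Auer-rod blasts and extramedullary disease, and the three CR categories add count and transfusion conditions. Only MLFS can be met at entry without any blood count recovery.
- **That DOR is contradictory because one visit can be both response and relapse.** Relapse is defined only after a response and speaks of blasts reappearing, which reads as a sequence. SAP Table 3, note 1, sets aside a single relapse followed by response, and a planned sensitivity analysis reverses that rule.
- **That the primary ORR should be redefined.** Data were analysed at the 2016 and 2017 cutoffs (SAP Section 12). The protocol also warns that transient blast increases can accompany recovery and that standard criteria may misjudge this drug class. A changed primary endpoint would be post hoc.

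**Conclusion.** The gap holds on the text, chiefly through MLFS: following the written rules, unchanged disease can be scored as a response. Its size is unknown. One such responder decides a result at exactly 42/125. If the other subjects' true rate is 25%, one to five raise the chance of passing from 1.9% to between 2.7% and 8.7%. Both statements rest on an assumed number of subjects, and the second also assumes that each is certain to be scored a responder.

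A reader might infer that the reported ORR is inflated. The documents do not show that, since nothing in them says that even one such subject enrolled. The point is worth acting on because the check is cheap and bears directly on the pivotal criterion. If no subject had baseline marrow blasts below 5%, the entry route is ruled out.

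**What to change.** Keep the primary ORR definition, and make three changes:

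1. **SAP Section 8.2.1, item 11.** Split the class below 20% so that baseline marrow blasts below 5% are shown separately.
2. **SAP Section 10.2.** Add a sensitivity analysis of the Phase 2 ORR and its 25% rule. AML subjects with baseline marrow blasts below 5% stay in the FAS denominator, but MLFS is not counted as a response for them. For all AML subjects, CR, CRi, CRp or MLFS at a visit with circulating blasts on the paired blood count is not counted. State that this analysis was added after the 2016 and 2017 analyses.
3. **Definitions.** The sponsor should reconcile the Phase 2 relapse definition with the response definitions in Protocol Table 7 and SAP Table 6.

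Marrow and blood blast counts are already collected, so the cost is SAP wording and a little programming. The downside is a sensitivity ORR that may be slightly lower than the primary one.

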**Table 8: Criteria for Stable Disease and Progressive Disease for Acute Myelogenous Leukemia**

Category	Response criteria
Stable disease	Failure to achieve a response and not meeting the criteria for disease progression
Disease progression (defined only for subjects who have previously attained PR or SD)	
Progression should be confirmed by 2 consecutive assessments separated by at least 1 month.
 
Development of new biopsy-confirmed extramedullary disease since last disease evaluation
 
The date of progressive disease is defined as the first date of progression.
 
Progression is defined as the following:
 
For patients with 5 to 67% bone marrow blasts at nadir:
 
 
- a >50% increase in bone marrow blast count percentage from the nadir and that is <math>\geq 20\%</math>.
 
 
For patients with <math>\geq 67\%</math> bone marrow blasts at nadir:
 
 
- a doubling of the nadir absolute peripheral blood blast count and the final absolute peripheral blood blast count is <math>> 10 \times 10^9/L</math>.
 

